12.3.3. Evaluation of the HIV reservoir in the blood

The quantification of total cell-associated HIV-DNA will be performed using the consensual real-time PCR method developed and implemented by the ANRS AC11 Quantification Group (limit of detection: 5 HIV-DNA copies/150 000 cells).

12.3.4. Minimal concentrations of ARVs in the plasma

At each visit, for all patients, a specific blood sample will be drawn and frozen to measure the minimal concentrations of all antiretroviral drugs including raltegravir and efavirenz. The precise date and hour of each blood collection will be strictly reported in the eCRF. The minimal concentrations of ARVs will be measured in case of virological failure in local laboratory and at the end of the study (plasma bank).

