- In the ANRS 163 ETRAL trial a sample bank will be constituted in order to monitor raltegravir and etravirine plasma concentrations. At specific points these concentrations will be analysed in correlation with trial end-points.

5.6 *Trial hypothesis*

Given the potency of raltegravir and etravirine, and although our limited clinical experience, we bring the hypothesis that a dual RAL/ETR regimen will be able to maintain the viral suppression if the two drugs are fully sensitive namely in patients naïve to both raltegravir and etravirine without any mutation that might impair drug's efficacy.

The second hypothesis is that, in a patient population with long-term ART, of at least 45 years of age, the switch to dual raltegravir/etravirine therapy should limit the long-term toxicity induced by NRTI and PI drugs, in particular cardiovascular, bone and renal diseases, without derogating from the key principle of sustained virological control.

ANRS 163 ETRAL trial should assess:

- The virological safety of raltegravir/etravirine association.
- The impact of the discontinuation of NRTIs, PIs on the distribution of adipose tissue, bone mineral density, metabolic parameters and seminal HIV-RNA viral load.

6 **OBJECTIVES**

6.1 *Principal objective*

To evaluate over 48 weeks of treatment the capacity to maintain virological success defined as the absence of 2 consecutive plasma viral loads (VL) > 50 copies/mL within 2 to 4 weeks of a dual raltegravir/etravirine regimen in HIV-1 infected patients, of at least 45 years of age, with suppressed plasma viremia switching from a boosted PI-containing regimen.

6.2 *Secondary Objectives*

6.2.1 *Biological efficacy*

- To assess the proportion of patients in therapeutic success up to week 48 and week 96
- To assess the proportion of patients with virological success (plasma HIV-RNA \leq 50 copies/mL) up to week 96
- To assess the proportion of patients with an interruption of therapeutic strategy
- To assess the proportion of patients with low grade virological failure (HIV-RNA plasma VL between 51 and 200 copies/mL) and the proportion of patients with high grade of virological failure defined as HIV-RNA >200 copies/mL at time of virological failure
- Time limit to virological failure
- HIV genotypic resistance profile, in plasma, in case of virological failure
- To determine the factors associated with virological rebound (plasma HIV-RNA > 50 copies/mL)

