7.2.2 Seminal sub-study

This sub-study will be proposed to 20 male patients of the centres located in the region of Ile-de-France (neighbourhood of Paris) to evaluate at W48 the potential suppressive effect of the dual raltegravir/etravirine regimen on the HIV-RNA seminal viral load; and the minimal concentrations (Cmin) of RAL and ETR in the seminal fluid.

[figure not shown]
Total sperm samples will be collected at home the day of the patient visit using the dedicated container delivered by the investigator during the previous visit and then transferred to the participating site within the 6 hours following sample collection.

Collected samples will be directly carried by the participant to “Service des maladies infectieuses”, department of the Pitié-Salpêtrière site.

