9.2 Secondary Endpoints

Biological efficacy

- Percentage of patients remaining in therapeutic success up to week 48 and week 96 defined as the absence of virological failure and the absence of treatment interruption due to adverse event judged by DSMB as related to the trial treatment or procedure
- Percentage of patients in virological success (plasma HIV-RNA \leq 50 copies/mL) up to week 96
- Percentage of patients with trial treatment interruption
- Percentage of patients with plasma HIV-RNA VL between 51 and 200 copies/mL and percentage of patients with plasma HIVRNA VL > 200 copies/mL at time of virological failure
- Median time of virological failure (time limit between the date of the study treatment initiation and the date of virological failure)
- Percentage of patients with RAL and/or ETR resistance mutations in case of virological failure and percentage of patients with resistant viruses to all study drug's class in case of virological failure
- Factors associated with the occurrence of plasma HIV-RNA VL > 50 copies/mL (genotype history, pre-cART VL, plasma drug concentration (etravirine, raltegravir) at the virological rebound, viral reservoir measured by HIV-DNA at D0 and adherence assessed with a self-questionnaire)
- Evolution of total cell-associated HIV-DNA from D0 to W48 and W96
- Evolution of CD4+, CD8+ T cells counts and CD4/CD8 ratio at each time point from D0

Tolerability and Metabolic Impact

- Percentage of patients with at least one serious adverse event as judged by DSMB as related to the trial treatment or to the trial strategy
- Percentage of patients with grade 3 or grade 4 clinical and biological adverse events
- Evolution of metabolic parameters (fasting triglycerides, total cholesterol, HDL-cholesterol, LDL-cholesterol and fasting glycemia)
- Evolution of the calibrated Framingham risk score and of the SCORE risk equation including HDL cholesterol (from the European Cardiovascular Society) from D0 to W48 and W96
- Evolution of renal function measured using proteinuria and the CKD-EPI (Chronic Kidney Disease Epidemiology Collaboration Calculator) formula to estimate the Glomerular Filtration Rate (GFR) from D0 to W96
- Evolution of limb lean, limb fat, visceral adipose tissue (VAT) and subcutaneous adipose tissue (SAT), measured by DXA scan (Dual-energy X-Ray Absorptiometry), from D0 to W48 and W96 (DXA scan sub-study, 80 patients)

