- Evolution of bone mineral density measured by DXA scans from D0, to W48 and W96 (DXA scan sub-study, 80 patients)
- HIV-RNA viral load and Cmin (Minimal Drug Concentration) of raltegravir and etravirine in seminal fluid at W48 (Seminal sub-study, 20 patients)
- Evolution of the inflammation markers (IL-6hs, sCD14, sCD163, D-Dimers, IP-10, IgG, CRPus and insulin) on frozen plasma aliquots from D0 to W48, and W96
- Evaluation of health-related quality of life with a self-assessment questionnaire from D0 to W48, and W96 and of the compliance with a self-assessment questionnaire at W-6/W-4, W48, and W96
-

Evaluation of metabolic impact according to the ovarian reserve and menopausal status

- between D0 and W48
- Comparison of metabolic (total cholesterol, LDL-cholesterol, HDL-cholesterol, triglycerides, non-HDL-cholesterol and triglyceride/HDL-cholesterol), inflammatory and innate immune activation (IL-6hs,

- sCD14, sCD163, D-Dimers, IP-10, IgG, CRPus and insulin), fat distribution and bone markers measured by DEXA scan between men and women at D0 et comparison of their evolution at W48
- Comparaison of the metabolic/inflammatory profile in women according to their ovarian reserve and menopausal status at D0 and its evolution up to week 48

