11 STUDY ASSESSMENTS AND CONDUCT

11.1 Schedule of assessments

	W-6/W-4	D0	W2	W4	W12	W24	W36	W48	W64	W80	W96	EOT
Informed Consent Signature	X											
Review eligibility criteria	X	X										
Collection of adverse events		X	X	X	X	X	X	X	X	X	X	X
Quality of life, felt symptoms		X						X			X	X
Adherence evaluation	X							X			X	X
Clinical exam (blood pressure, heart rate, body temperature, weight and targeted physical examination)	X ¹	X ^{2,3,4}	X	X	X	X	X	X ^{2,3,4}	X	X	X ^{2,3,4}	X ²
HBV/HCV serology	X											
Urinary pregnancy test If positive: β HCG ⁵	X	X ⁶	X ⁶	X ⁶	X ⁶	X ⁶	X ⁶	X ⁶	X ⁶	X ⁶	X ⁶	X ⁶
HIV-RNA plasma Viral Load⁷	X	X		X ⁸	X ⁸	X ⁸	X ⁸	X ⁸	X ⁸	X ⁸	X ⁸	X ⁸
CD4/CD8 Lymphocytes	X	X			X	X		X		X	X	X
Whole blood cells count	X					X		X		X	X	X
Creatinine, AST, ALT, CPK, bilirubin, urine analysis⁹	X			X	X	X		X		X	X	X
Lipid profile¹⁰, fasting glycemia		X			X	X		X			X	X
Genotypic resistance on blood DNA	X											
DXA-Scan sub-study¹¹		X						X			X	
Seminal sub-study¹²								X				
Study drug prescription		X		X	X	X	X	X	X	X		
Sample bank¹³												
Plasma bank: minimal plasma ARV concentration, virological analysis		X	X	X	X	X	X	X	X	X	X	X
Whole blood bank: Total cell-associated HIV-DNA		X						X			X	X
Plasma and serum bank: Immunologic analysis of inflammation markers¹⁴		X						X			X	X

¹ Electrocardiogram (ECG)

² Anthropometric measurements (abdominal and waist circumference)

³ Cardiovascular risk factors: arterial hypertension, tobacco, alcohol abuse, physical activity, diabetes

⁴ Measurement of the systolic blood pressure at D0 W48 W96 according to the recommendations (Pickering et al. Circulation 2005, in Appendix A7)

⁵ Only for women of childbearing potential

⁶ Only in case of suspicion

⁷ Plasma viral loads using a routine technique with a positivity threshold of maximum 50 copies/mL

⁸ If HIV-RNA plasma viral loads > 50 copies/mL an additional blood collection have to be performed, within an interval of two to four weeks, to confirm the virological rebound. If the virological failure is confirmed, a resistance genotype and a dosage of ARV drugs concentration in plasma will be performed on the second HIV-RNA plasma VL test. A plasma bank should also be done

⁹ Urine analysis: proteinuria, albuminuria, creatininuria, glycosuria

¹⁰ Lipid profile: fasting triglycerides, total cholesterol, HDL-cholesterol, LDL-cholesterol

¹¹ DXA-scan sub-study: evolution of the Bone Mineral Density (BMD) and of the body fat distribution in 80 patients

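### Drug concentrations are called minimal (plasma) or Cmin (semen), but the protocol does not require the hour of the last dose, nor the hour of semen collection, so values cannot be identified as troughs.

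*Combined protocol and SAP*

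**What the plan says.** **Plasma.** Section 12.3.4 provides, for every participant and every visit, that "a specific blood sample will be drawn and frozen to measure the minimal concentrations of all antiretroviral drugs including raltegravir and efavirenz". The timing requirement that follows is "The precise date and hour of each blood collection will be strictly reported in the eCRF". The schedule in section 11.1 (repeated in section 4) labels the bank "Plasma bank: minimal plasma ARV concentration, virological analysis" from D0 to W96 and at EOT, with no footnote on dose timing. Section 12.3.4 places the assays at virological failure and at the end of the study.

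**Semen.** Section 7.2.2 sets out to evaluate at W48 "the minimal concentrations (Cmin) of RAL and ETR in the seminal fluid", and section 9.2 lists this as a secondary endpoint in 20 patients. The sample is produced at home on the day of the visit and must reach the site within 6 hours (sections 7.2.2 and 11.5.1).

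**Use of the values.** Section 9.2 lists "plasma drug concentration (etravirine, raltegravir) at the virological rebound" among the candidate factors for a viral load above 50 copies/mL. Section 5.5.2 adds: "At specific points these concentrations will be analysed in correlation with trial end-points". At virological failure, section 11.11.1 has the concentration measured on the confirmatory viral-load sample.

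**Dosing.** Section 10.1 gives both drugs twice daily, after a meal. The visit descriptions in sections 11.4 and 11.5 ask the investigator to check treatment intake. They do not ask when the last dose was taken.

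**The concern.** A trough is defined by the time since the last dose, not by the time of day. Section 5.5.2 uses it in that sense when it cites raltegravir concentrations at 12 hours. To know whether a sample is a trough, one needs the collection time and the time of the preceding intake. For plasma the protocol requires only the first; for semen it requires neither.

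Two planned analyses are exposed. The seminal Cmin endpoint may mix trough and non-trough values. The comparison of plasma concentrations at rebound would carry variation that reflects when the patient took the last tablet rather than overall exposure. An intake time that was not collected cannot be reconstructed at the analysis stage.

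**Working it through.** The protocol gives no figure to reproduce here. The check is a reading of the sampling provisions, followed by an illustration of size.

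**Step 1: what is required for each sample.**

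| Sample | Collection hour required | Last-intake hour required | Pre-dose draw or post-dose window |
|---|---|---|---|
| Banked plasma (11.1, 12.3.4) | Yes | No | None |
| Confirmatory viral-load sample used for concentration (11.11.1) | Yes, if 12.3.4 is read as covering it | No | None |
| Semen at W48 (7.2.2, 11.5.1) | No | No | None |

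**Step 2: can the time since dose be recovered?** With h = collection time minus last-intake time, plasma has one of the two terms and semen has neither. Twice-daily dosing gives a nominal interval of 24/2 = 12 h, and nothing in the protocol fixes where in that interval a clinic sample falls. For semen, the permitted delay of up to 6 h between collection and the site is itself 6/12 = half of a dosing interval.

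**Step 3: how large the error could be.** The documents give no half-life, so this is an assumption, shown for 3, 9 and 40 h. With mono-exponential decline, the concentration at h hours relative to the 12 h trough is

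ratio = 2^((12 − h) / half-life)

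| Hours since intake | Half-life 3 h | Half-life 9 h | Half-life 40 h |
|---|---|---|---|
| 4 | 2^(8/3) = 6.35 | 2^(8/9) = 1.85 | 2^(8/40) = 1.15 |
| 8 | 2^(4/3) = 2.52 | 2^(4/9) = 1.36 | 2^(4/40) = 1.07 |
| 12 | 1.00 | 1.00 | 1.00 |

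The error runs from several-fold to a few per cent. If semen followed the same decline (a further assumption), the 6 h uncertainty in collection time alone would correspond to 2^(6/3) = 4.0, 2^(6/9) = 1.59 and 2^(6/40) = 1.11.

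**The case against.** **The eCRF and the sample procedure are not in the documents, and either might capture dose time.** The check of treatment intake could record it in practice, so the supportable statement is that the protocol does not require it. That does not remove the gap: section 12.4.1 describes the separate procedure as covering handling and shipment, and section 12.3.4 specifies only the draw time. If a dose-time field exists, citing it in 12.3.4 settles the plasma part.

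**Fasting visits might amount to pre-dose sampling**, since the drugs follow a meal. This helps at some visits only. W2, W36, W64 and W80 have a plasma bank and no lipid profile, the confirmatory draw has no fasting condition, and the hour of the previous dose stays unknown even in a fasting patient.

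**Stronger readings that the documents do not support:**

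- *Plasma Cmin is a listed endpoint.* It is not. The listed Cmin endpoint is seminal; plasma concentration enters as a candidate factor for rebound.
- *Timing error exceeds the raltegravir–etravirine interaction.* Section 5.5.2 cites a 34 % fall in raltegravir C12, a ratio of 1/(1 − 0.34) = 1.52. A 4 h sample exceeds that only if the half-life is below 8/log2(1.52), about 13 h; at 9 h, an 8 h sample (1.36) does not. The 34 % is also healthy-volunteer background data, and this single-arm trial plans no contrast of raltegravir with and without etravirine.
- *Mis-timing could reverse the association with rebound.* No mechanism for this appears. Timing noise unrelated to outcome would be expected to weaken an association.
- *Dose times would expose non-adherence.* A patient who misses doses but takes one about 12 h before the visit would still fall inside any window.

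**Much is already collected.** Appendix A8 states that patient samples have been collected and stored. For those without an intake time the remedy reduces to labelling, which is still worthwhile because section 12.3.4 leaves the banked assays to the end of the study and section 16.2.3 requires a detailed SAP before any analysis.

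**Conclusion.** The point stands in limited form. From the data the protocol requires, neither plasma nor semen values can be identified as troughs, and the gap is wider for semen, where Cmin is the listed endpoint. The consequence is timing noise in a 20-patient sub-study endpoint and in the exploratory analysis of concentration at rebound. The primary endpoint does not use these values.

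The classification problem does not depend on the half-life; its size does. At 4 h after intake the overstatement ranges from about 6.3-fold (3 h half-life) to 1.15-fold (40 h), under an assumed mono-exponential decline. No single figure applies to both drugs on these documents. The conclusion would change if the eCRF already records the hour of last intake and, for semen, the hour of collection.

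**What to change.** **Data collection (12.3.4, 7.2.2 and the eCRF).** Record the date and hour of the last raltegravir and last etravirine intake for each post-baseline banked plasma sample, each confirmatory viral-load sample used for drug concentration, and each semen sample. Record the semen collection hour as well. The D0 bank is left out because it precedes the first trial dose.

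**Analysis (SAP).** Pre-set a post-intake window around the end of the 12 h interval within which a value counts as Cmin. Report every other value, including samples already banked without an intake time, as an untimed concentration, and keep those out of any summary labelled Cmin.

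**Wording.** Section 12.3.4 refers to a sample to "measure the minimal concentrations of all antiretroviral drugs including raltegravir and efavirenz", whereas the regimen in section 10.1 is raltegravir plus etravirine. The two sections should be reconciled. This is a separate editorial matter and adds no weight to the timing point.

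**Cost.** A few eCRF fields and a short SAP rule. The price is that fewer samples qualify as Cmin, which matters most in the 20-patient seminal sub-study. For samples already stored, only the labelling rule can be applied unless intake times were noted at the time.

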12.4 Centralization of samples in Inserm-ANRS Biobank

12.4.1 Centralization at CRB CHU Bordeaux-Pellegrin (France)

Blood samples are collected at the trial site. The trial site is responsible for cytopreservation, separation and storage of all samples collected at the trial site as prescribed by the protocol.

The samples which have to be transported to central laboratories or to a central biobank, are stored at the trial site until shipment. The handling and shipment of these samples is detailed in a separate document (trial specific SOP (Standard Operating Procedure)). Blood samples will be centralized in the Biobank at CRB (CHU Bordeaux-Pellegrin, France).

All laboratories involved shall use the human materials sampled in the trial only in accordance with the agreed protocol, the international Good Clinical Practice principles as laid down by the ICH Harmonised Tripartite Guidelines for Good Clinical Practice (ICH GCP), the EU Clinical Study Directive and relevant other legislation or regulatory requirements as may be required in the country.

The CMG project manager shall supply trial sites with guidance on handling and storage of the materials, and other related relevant information.

All proposals for additional laboratory assessments that are not specified in this protocol must be submitted to the Study Steering Committee and approved prior to their implementation.

12.4.2 Samples access

Samples centralized at CRB should exclusively be used to:

- confirm the results obtained during the research authorized by the Scientific Committee,
- perform studies already planned according to the protocol,
- further studies not initially foreseen in the protocol and in accordance with procedures established by the Scientific Committee. For studies outside the field of investigation specified in the participants' information consent, an Ethics Committee approval and if appropriate, a new consent will be required.

These samples will be used according to procedures set up by INSERM SC10-US019. Before extraction of samples for analysis, sampling, recipients and deadlines will have been decided by the Scientific Committee.

At the end of the trial, six months after the last visit of the last participant, biological samples will be included in the Inserm-ANRS biobank, authorized for their total or partial transfer for scientific use, except in case of disagreement by each participant. Samples will no longer be available to the the scientific committee, but remain under the responsibility of the Inserm-ANRS. Strict adherence to the participants' rights to refuse further use of this biobank is guaranteed.

13 TRIAL SAFETY

13.1 Definitions

13.1.1 Adverse Event (AE)

Any untoward medical occurrence in a patient or a clinical trial subject administered a medicinal product and which does not necessarily have a causal relationship with the treatment or the research.

13.1.2 Adverse Reaction (AR)

All untoward and unintended responses to an investigational medicinal product related to any dose administered or to the research (e.g. trial procedures, trial treatments).

13.1.3 Serious Adverse Event (SAE) or Serious Adverse Reaction (SAR)

Any untoward medical occurrence or effect that at any dose:

- results in death;
- is life-threatening (means that the subject was at immediate risk of death at the time of the event; it does not refer to an event which hypothetically might have caused death if it were more severe);
- requires hospitalization or prolongation of existing hospitalization;
- results in persistent or significant disability or incapacity;
- is a congenital anomaly or birth defect;
- is a grade 3 or 4 clinical or biological adverse event;
- is an important medical event that, when based upon appropriate medical judgment may jeopardize the subject and may require medical or surgical intervention to prevent one of the outcomes listed above in the definition for a serious adverse event;

Examples of such events include allergic bronchospasm requiring intensive treatment at an emergency room or at home, blood dyscrasias, convulsions those do not result in inpatient hospitalization, development of drug dependency or drug abuse, or suspected transmission of an infectious agent via a medicinal product...

EXCEPTIONS: SAE not requiring immediate reporting to the sponsor

- Hospitalizations or prolongation of existing hospitalizations that are not considered as serious:
 - outpatient care: the patient has been formally admitted to a hospital for medical reasons with no seriousness criteria (described above) and does not require overnight hospitalization;
 - elective or previously scheduled surgery or medical treatment;
 - hospitalization for social or administrative reasons;
 - pre-specified trial hospitalization for observation.
- Pre-existing biological abnormalities or diseases or conditions present or detected prior to start of study drug administration that do not worsen.

13.1.4 Suspected Unexpected Serious Adverse Reaction (SUSAR)

An adverse reaction, the nature, the outcome or severity of which is not consistent with the applicable product Reference Safety Information (Summary of the Product Characteristics, SmPC, for the study drugs) or the applicable trial procedures information noted in the protocol.

